#### **5.8.4 Lost to follow-up**

A participant will be considered as lost to follow-up if he/she repeatedly fails to return for scheduled visits and is unable to be contacted by the site.

The site must take preventive measures to avoid a participant being lost to follow-up (e.g., document different ways of contact, such as telephone number, home address, email address, contact person if the participant cannot be reached).

The following actions must be taken if a participant fails to return to the site for a scheduled study visit:

- The site staff must attempt to contact the participant and reschedule the missed visit as soon as possible and counsel the participant on the importance of maintaining the assigned visit schedule and ascertain if the participant wishes to and/or should continue in the study.
- If the participant cannot be reached, the site must make a reasonable effort to contact the participant and document all attempts in the participant's medical chart. Reasonable efforts include, when possible, 3 telephone calls to the last available telephone number and 1 registered/certified letter to the participant's last known mailing address or local equivalent methods.
- If the participant is still unreachable after all contact attempts listed above, he/she will be considered lost to follow-up.

The date of last successful contact with the participant will be collected in the eCRF.

## **6 TREATMENTS**

### **6.1 Study treatment**

#### **6.1.1 Investigational treatment**

Cenerimod is supplied as film-coated tablets at a 4 mg dose.

The inactive ingredients of the cenerimod film-coated tablet formulation are: hydroxypropyl methylcellulose, polyvinylpyrrolidone, mannitol, colloidal silicon dioxide, and magnesium stearate. The film coating consists of hydroxypropyl methylcellulose, propylene glycol, titanium dioxide, iron oxide yellow, iron oxide red, and iron oxide black.

### **6.1.2 Study treatment dosing and administration**

One tablet of cenerimod will be taken orally irrespective of food intake. The tablet will be swallowed whole. It is preferable that the tablet is taken each day in the morning.

Participants must be instructed not to take study treatment in the morning of study visit days. On the day of the study visits, study treatment must be administered only after the completion of the pre-dose assessments (i.e., vital signs, ECGs, laboratory tests, and PK sampling). The dose prior to the Month 2 visit must be administered by the participant 24 h ( $\pm 3$  h) prior to the anticipated dosing at the Month 2 visit. Date and time of study treatment intake will be recorded in the eCRF for Day 1, the day before Month 2, and Month 2.

To ensure compliance, the study personnel must remind participants at each visit of the study treatment intake requirements.

#### **6.1.2.1 Study treatment dose adjustments**

Study treatment dose adjustments are not permitted.

Note that under **no circumstances** should a participant take more than 1 tablet per day.

### **6.1.3 Justification for dose**

The selection of a 4 mg (o.d.) dose of cenerimod for this study is based on the safety and efficacy results from the Phase 2b study (ID-064A202), where cenerimod did not show any safety signals/concerns at any tested dose (0.5, 1, 2, and 4 mg), and was not associated with any clinically relevant safety findings. In that study, cenerimod 4 mg was well tolerated and was the only dose to show a clinically significant reduction on the primary endpoint (change from baseline to Month 6 in mSLEDAI-2K score) [Cenerimod IB, section 5.3.1.2]. These results are in line with those of the anifrolumab Phase 3 study (TULIP-1) conducted in SLE patients and using similar endpoints [Furie 2019].

### **6.1.4 Treatment assignment**

All participants will receive cenerimod. An IRT system will be used to assign the kit numbers to the individual participants.

### **6.1.5 Study treatment handling/preparation/storage/accountability**

Manufacture, labeling, packaging, and supply of study treatments is conducted according to Good Manufacturing Practice.

All study treatment supplies are to be used only in accordance with this protocol, and not for any other purpose.

#### ***6.1.5.1 Study treatment packaging and labeling***

Study treatment is provided as tablets and supplied in childproof bottles.

Study treatment is labeled to comply with the applicable laws and regulations of the countries in which the study sites are located.

#### ***6.1.5.2 Study treatment distribution and storage***

Study treatment supplies must be kept in an appropriate, secure area and stored according to the conditions specified on the label. The storage conditions must be explained to the participant.

#### ***6.1.5.3 Study treatment dispensing***

The participants will receive sufficient study treatment to cover the period up to the next scheduled visit. Participants are asked to return all used, partially used, and unused study treatment bottles at each visit. Should the treatment bottle dispensed at a scheduled visit be lost or damaged, a replacement bottle can be requested via the IRT system.

Protocol-mandated study treatment dispensing procedures may not be altered without prior written approval from the sponsor. In exceptional circumstances (e.g., if the participant lost the study treatment between 2 visits, or if the participant is unable to return to the site due to a medical emergency / hospitalization at another hospital / long distance to travel / pandemic restrictions), unscheduled dispensing and delivery of study treatment may occur outside of a scheduled visit.

An accurate record of the date and amount of study treatment dispensed to each participant must be available for inspection at any time.

#### ***6.1.5.4 Study treatment accountability***

The inventory of study treatment dispensed to and returned by the participant (i.e., study treatment accountability) must be performed by site personnel on the day of the visit and before dispensing further study treatment. The inventory is to be recorded by site personnel in the site documentation and in the eCRF. The study treatment accountability log in the eCRF will include the following information for each study treatment bottle dispensed to the participant:

- Dispensed bottles number.
- Date dispensed / number of tablets dispensed.
- Date returned / number of tablets returned.

All study treatment supplies, including partially used or empty bottles must be retained at the site.

If the participant forgets to bring the remaining study treatment to a study visit, he/she must be instructed to not take any tablets from the remaining study treatment bottle and to return it at the next visit.

#### **6.1.5.5 Study treatment return and destruction**

On an ongoing basis and/or upon termination of the study, the CRA will collect used and unused treatment kits, which will be sent to the warehouse, where the sponsor / depot personnel or a deputy will check treatment reconciliation.

In certain circumstances (e.g., local hospital procedures), used and unused study treatment containers may be destroyed at the site. In general, this can only be done once study treatment accountability is finalized and has been checked by the sponsor personnel representative, and written permission for destruction has been obtained from the sponsor. Exceptions might occur if a local process requires immediate destruction of the study treatment. Such local study treatment destruction processes must be provided and approved by the sponsor.

#### **6.1.6 Study treatment compliance**

Study treatment compliance with the prescribed study treatment dose regimen is based on study treatment accountability. Study treatment compliance will be calculated by site personnel at each monthly visit during the study treatment period using the formula below:

Compliance = [(number of tablets dispensed – number of tablets returned) / total number of tablets that should have been taken during the period\*] × 100

\*The period is defined as the number of days between the respective visits.

During the entire study treatment period, the study treatment compliance is expected to be 80% or above. At each monthly visit during the study treatment period, the study treatment compliance is also expected to be 80% or above. If below 80% without a medical justification (e.g., AE), this will be considered as a protocol deviation.

The investigator/delegate must discuss the non-compliance with the participant to clarify the reason(s) and to take appropriate actions to avoid re-occurrence. This discussion and its outcome must be documented in the source documents.

#### **6.2 Previous and concomitant medications**

A previous therapy is any treatment for which the end date is prior to start of study treatment. Relevant previous therapies (e.g., SLE treatment) for which the end date is less than 12 months prior to ICF signature will be recorded in the eCRF.

A study-concomitant therapy is any treatment (including methods of contraception and traditional and alternative medicines, i.e., plant-, animal-, or mineral-based medicines) given for any reason including the background SLE therapy that is either ongoing at the start of study treatment or is initiated during the study treatment period, or during the follow-up period up to FSV. All study-concomitant therapies administered will be reported in the eCRF.

The generic name, start/end dates of administration (as well as whether it started prior to first study treatment administration and/or was ongoing at FSV), route, dose, frequency, and indication for use will be recorded in the eCRF.

### **6.2.1 Auxiliary medicinal products**

An auxiliary medicinal product is a medicinal product used for the purpose of the clinical study but not as an Investigational Medicinal Product (e.g., a mandatory background therapy or a medicinal product used for a study-mandated procedure).

Auxiliary therapy includes background SLE therapy as requested for a participant to be eligible in the study. Any post-Day 1 change of background medication has the potential to obviate the treatment effect and efforts should be made to adjust background medication during the screening period.

Allowed auxiliary therapy	Conditions of use
Antimalarials (hydroxychloroquine, chloroquine, quinacrine)	See Section 6.2.1.1
Mycophenolate mofetil / mycophenolic acid	
Azathioprine	
Methotrexate	
Belimumab	
Telitacicept	
OCS background therapy	See Section 6.2.1.2

#### **6.2.1.1 SLE background therapy (except OCS background therapy) conditions of use**

For eligibility, SLE background medication must have been started at least 90 days prior to Screening.

Dose, frequency, and route of administration must be stable for at least 30 days prior to Day 1.

[figure not shown]
Treatment, dose, and route of administration should remain identical from Day 1 to the completion of Visit 14 (Month 12).

The dose may be decreased by the investigator/delegate for toxicity reasons, or to optimize management of an AE, such as an infection. The toxicity/event must be reported as an AE and the change of dose entered in the eCRF. The dose can be returned to the Day 1 level if the toxicity/event resolves and as clinically indicated.

Antimalarials/immunosuppressants (including dose, frequency, and route of administration) should not be changed if a participant has increased SLE disease activity during the OCS tapering period.

#### **6.2.1.2 OCS background therapy conditions of use**

**Figure 4 OCS management overview**

CS = corticosteroid(s); OCS = oral corticosteroid(s).

##### **6.2.1.2.1 OCS eligibility criteria**

- OCS must have been started at least 30 days prior to Screening.
- Participants will be eligible at Screening and Day 1 under the following conditions:
  - when OCS is the only SLE background medication:  $\geq 7.5$  mg/day and  $\leq 30$  mg/day prednisone or equivalent.
  - when OCS is not the only SLE background medication:  $\leq 30$  mg/day prednisone or equivalent.

##### **6.2.1.2.2 OCS management and dose optimization during Screening (Visit 1 up to Visit 2)**

For the purpose of standardization, it is recommended to use either prednisone, methylprednisolone, or prednisolone during the study [see Appendix 12]. If a participant is treated with another background OCS therapy, it is recommended to switch to 1 of the 3 OCS mentioned above during the Screening period.

For participants treated with OCS prior to enrollment, it is recommended to optimize the background OCS therapy during the Screening period to the minimal effective dose by performing a cautious tapering [Table 6]. This will allow for minimal OCS changes during the treatment period outside of the mandatory OCS tapering period (Visit 5 up to Visit 10), which is the preferred approach.

Dose reductions are at the investigator's discretion; however, the OCS dose must be kept stable for 15 days prior to Day 1.

#### *6.2.1.2.3 OCS management during treatment period*

The OCS dose should be kept stable. Any change in the OCS dose should be restricted to 2 different situations: a) medically justified safety reason and b) protocol-specified rules (see below). The justification and nature of any change should be thoroughly documented in the participants' medical records.

#### **Protocol-specified rules for changes in OCS dose**

##### ***From Visit 2 up to Visit 5: Recommended stable OCS dose***

The OCS dose should be kept stable. The investigator is encouraged to only change the OCS dose in the following situation:

- OCS dose decrease is allowed for participants with SLE disease activity improvement for at least 4 consecutive weeks (i.e., between 2 consecutive visits), but is not mandatory. Table 6 describes a recommended tapering schedule. SLE disease activity improvement is defined as BILAG reduction of all A scores to B/C/D scores and reduction of all B scores to C/D scores, and no score worsening in other organ systems, as defined by  $\geq 1$  new A score or  $\geq 2$  new B score.

##### ***From Visit 5 up to Visit 10: Mandatory OCS tapering***

For participants with an OCS dose  $\geq 10$  mg/day at Day 1, steroid tapering to an OCS dose of  $\leq 7.5$  mg/day MUST be attempted [see the recommended tapering schedule in Table 6] and started within 14 days after Visit 5.

Tapering should not be attempted if at least 1 of the following criteria is met:

- Worsening of SLE disease activity defined as  $\geq 1$  new BILAG A or  $\geq 2$  new BILAG B scores (except mucocutaneous and musculoskeletal domains).
- Moderate-to-severe skin disease as reflected by a CLASI activity score of  $\geq 10$ .
- Moderate-to-severe arthritis disease as reflected by an active joint count of  $\geq 4$  tender and/or swollen joints.

If a participant fails tapering down at the first attempt, an increase of the OCS dose up to the dose before the start of the forced tapering is allowed. Another attempt to taper down OCS might be done unless at least 1 of the above criteria is met.

If steroid tapering is not attempted in an eligible participant, the sponsor must be contacted immediately. The recommended steroid-tapering regimen is provided in Table 6, but due to variability in participant responses to steroid treatment and tolerability of taper, investigators will have flexibility in how the OCS dose is reduced at each visit.

Investigators will not be required but may continue to taper OCS dose beyond 7.5 mg/day up to Visit 10.

Steroid tapering will not be permitted after Visit 10. The dose may be optimized for 14 days after Visit 9 but the OCS dose must be stable for 14 days prior to the scheduled Visit 10.

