#### **7.2.2.2 *British Isles Lupus Assessment Group***

The BILAG will be assessed by the investigator or delegate as per the schedule of assessments [see Section 1.3].

The scoring system for the BILAG index of disease activity is based upon the principle of the physician's intention to treat, and the main feature of the BILAG index is that disease activity in different organs/systems is reported separately. The investigator will record clinical features covered by the BILAG index of lupus disease activity and relevant data will be recorded in the BILAG form. There are 9 systems: constitutional, mucocutaneous, neuropsychiatric, musculoskeletal, cardiorespiratory, gastrointestinal, ophthalmic, renal, and hematological. Immunological data do not contribute to BILAG scores, but basic hematology and assessment of renal function determine the scores of the relevant systems [see Appendix 7]. As cenerimod causes a reduction in the peripheral blood lymphocyte count, and hence the complete WBC count, these data will not contribute to the scoring.

A score is calculated for each system depending on the clinical features present and whether they are "not present", "new", "worse", "the same" or "improving" in the last 4 weeks compared to previous assessment. Of note, the "improving" score MUST respect the following definition:

- The amount of improvement is sufficient for consideration of reduction in therapy and would not justify escalation in therapy,  
*and*
- Improvement must be **present currently and for at least 2 weeks** out of the last 4 weeks,  
*or*
- The manifestation has **completely resolved and remained absent over the whole last 1 week**.

The scoring categorizes disease activity into 5 different grades from A to E:

- Grade A represents very active disease requiring a prednisone dose of > 20 mg/day or equivalent and/or immunosuppressive drugs.
- Grade B represents moderate disease activity requiring a prednisone dose of < 20 mg/day or equivalent, topical steroids, topical immunosuppressives, antimalarials, or NSAIDs.
- Grade C represents mild stable disease.
- Grade D represents no current disease activity, but the system has been previously affected.
- Grade E represents no current or previous disease activity.

Important extensions of selected BILAG glossary and SLEDAI-2K clinical variable definitions are detailed below. Of note, protocol-specific extensions for BILAG are highlighted in italic below:

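### On its natural reading, the BILAG exemption from the mandatory steroid taper leaves out new musculoskeletal A grades, and the joint-count substitute does not cover grade A arthritis in only 2 or 3 joints

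*Combined protocol and SAP*

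**What the plan says.** The rule is in section 6.2.1.2.3, under the Visit 5 to Visit 10 heading, and is repeated in the synopsis. Anyone on 10 mg/day or more of prednisone equivalent at Day 1 must attempt a taper to 7.5 mg/day or less, starting within 14 days of Visit 5. Going lower is optional: "Investigators will not be required but may continue to taper OCS dose beyond 7.5 mg/day up to Visit 10".

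The taper is not to be attempted if any one of three criteria holds:

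1. At least one new BILAG A, or at least two "new BILAG B scores (except mucocutaneous and musculoskeletal domains" (the bracket closes there).
2. A CLASI activity score of 10 or more.
3. "Moderate-to-severe arthritis disease as reflected by an active joint count of" 4 or more tender and/or swollen joints.

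If the taper is not started, the text says: "If steroid tapering is not attempted in an eligible participant, the sponsor must be contacted immediately".

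Section 7.2.2.2 describes the top grade: "Grade A represents very active disease requiring a prednisone dose of > 20 mg/day or equivalent and/or immunosuppressive drugs". For the musculoskeletal domain it allows grade A arthritis from observed synovitis in 2 or more joints, with marked loss of movement and loss of independence in basic daily activities. Section 6.2.1.1 adds that antimalarials and immunosuppressants "should not be changed if a participant has increased SLE disease activity during the OCS tapering period".

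**The concern.** The bracket follows the noun that the A and B limbs share. The next two criteria are a skin measure and a joint measure, one for each excepted domain. The natural reading is therefore that BILAG grades in those domains, A as well as B, are set aside and replaced by CLASI and the joint count. The joint count is not a full replacement, because its threshold is 4 joints and grade A arthritis can arise from 2.

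On that reading, a participant with new, disabling arthritis in a few joints at Visit 5 must still attempt a steroid reduction, while the background immunosuppressants are held fixed. What is at stake is that participant's safety and, secondarily, how the OCS-change and response summaries are read. No sample size, error rate or primary analysis is involved.

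The protocol words a similar test without a domain exception elsewhere. For the optional taper between Visits 2 and 5 it requires "no score worsening in other organ systems, as defined by" one or more new A or two or more new B scores. That taper is voluntary and conditional on improvement, so a stricter entry test is to be expected. The comparison shows only that the exception is particular to the mandatory taper.

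**Working it through.** The plan states no figure to reproduce. The check runs the three criteria against the participant in question under each reading of the bracket.

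**Inputs.** OCS of 10 mg/day or more at Day 1 (6.2.1.2.3). New musculoskeletal grade A from severe arthritis, minimum 2 joints (7.2.2.2; that definition is worded for the Screening visit, and applying it at Visit 5 is an assumption). No other new A or B grade. CLASI activity below 10. Number of tender and/or swollen joints *j*, out of the 28 assessed (7.2.2.6).

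**Rule.** Exempt if criterion 1, 2 or 3 is met. Criterion 2 is not met by construction. Criterion 3 is met when *j* ≥ 4. Criterion 1 is met only if a musculoskeletal A grade counts.

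| Joints *j* | Bracket covers A and B | Bracket covers B only |
|---|---|---|
| 2 | taper must be attempted | exempt |
| 3 | taper must be attempted | exempt |
| 4 or more | exempt | exempt |

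The arthritis gap on the natural reading is exactly *j* = 2 or 3. On the B-only reading it is empty.

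**Non-joint disease.** Appendix 7 lists severe myositis as a musculoskeletal item. Myositis adds 0 to the joint count and 0 to CLASI, so if it grades A it would also be uncovered. The rule that turns that item into a grade is not in the documents, so this stays conditional. No gap is asserted for the skin domain.

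**Dose against the grade A description.** First step in Table 6 (days 0–14; the schedule is an example and the pace is flexible):

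| Starting dose, mg/day | After first step | Crosses from above 20 to 20 or below? |
|---|---|---|
| 30 | 20 | yes |
| 25 | 20 | yes |
| 20 | 15 | no, already at 20 |
| 15 | 12.5 | no, already below |
| 10 | 7.5 | no, already below |

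Only the 25 and 30 mg/day starters are moved by the taper from above the dose named for grade A to 20 mg/day or below. The size of the Table 6 steps applies to everyone who tapers and does not measure the gap.

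**The case against.** The strongest objection is that grammar leaves the bracket open. It sits directly after the B limb and could qualify B scores alone, in which case new A grades in every domain already block the taper. That stands as a possibility. The paired skin and joint criteria favour the wider reading without settling it, and sites could apply the rule differently.

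The second objection is that the case is narrow. It needs new grade A arthritis with functional loss, fewer than 4 tender or swollen joints, CLASI below 10 and no other qualifying worsening. Joints that are merely tender count towards the 4. If the active joint count were a sum of tender and swollen joints (Appendix 11 records a total of both), 2 joints that are each tender and swollen would give 2 + 2 = 4 and be exempt. The criterion's wording reads as a count of joints, but the point narrows the gap further.

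The third objection is that safeguards exist. A dose change is allowed for a "medically justified safety reason"; the pace is flexible; the pre-taper dose may be restored after a failed attempt, and a second attempt is optional. One burst of up to 40 mg/day for up to 14 days is allowed between Visits 2 and 10 (6.2.2.1), which exceeds the grade A dose. Section 10.7 permits a deviation to remove an immediate hazard. These soften the consequence. None is a listed exemption, sponsor contact is a notification, and section 10.7 otherwise rules out prospective waivers.

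Finally, the skin and joint criteria are absolute levels, so they also protect persistent disease that a test for new grades would miss. That is correct and is a reason to keep them.

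**Conclusion.** The point holds in a limited form. On the natural reading, new grade A arthritis with 2 or 3 affected joints does not exempt a participant from attempting the mandatory taper, although the protocol describes grade A as very active disease. This rests on two assumptions: that the bracket covers A as well as B scores, and that the 2-joint definition applies at Visit 5. If the first fails, only an ambiguity remains.

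The case is uncommon. With about 15 participants and no frequency in the documents, no expected number can be given.

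A reader might infer more than this. That the plan leaves such a participant without recourse is not supported, given the safeguards. That the taper takes every participant below the dose grade A needs is not supported either: starters on 20 mg/day or less are not above that dose to begin with, and the grade A description names immunosuppressive drugs as an alternative or addition to the steroid dose. A definite gap for myositis or for skin disease cannot be shown, because the documents do not give the grading rules.

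Confidence is medium. This is a cheap improvement to participant protection and does not threaten the primary objectives.

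**What to change.** Reword the first exemption in section 6.2.1.2.3 and in the synopsis to: *at least one new BILAG A score in any domain, or at least two new BILAG B scores (B scores in the mucocutaneous and musculoskeletal domains excepted)*. Leave the CLASI and joint-count criteria unchanged.

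The cost is one clause in two places. BILAG is already assessed at Visit 5, so no data are added, and the current amendment reports that nobody has been enrolled. The downside is possibly a few fewer tapers and slightly less information on OCS reduction. If the B-only meaning was intended, the change alters nothing in practice and makes the rule read the same at every site.
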